3.1.4 Screening Values

For the tables and figures, a patient's screening value is defined as the most recent non-missing value with a visit value of "Screening". In the listings, all values which have a visit of "Screening" will be presented.

3.1.5 Handling of Missing/Incomplete Values

Unless otherwise explicitly specified, missing data will not be imputed; observed cases will be used in the analyses.

If a non-numeric clinical laboratory value is reported for an endpoint of the form "< X.XX", "≤ X.XX", ">X.XX", or "≥X.XX" and the endpoint is being summarized as a numeric quantitatively (i.e., assuming the endpoint response is numeric) the numeric value portion of the result being reported will be imputed. As a specific example, for the sRBC lysis endpoint non-numeric values of "<2.00" and ">100.00" may be reported; in these in these instances the values of 2.00 and 100.00, respectively, will be imputed.

Note that this convention will not apply to PK concentration data which is below the lower limit of quantification (i.e., <LLOQ). For PK concentration summary statistics values below the lower limit of quantification will be set to zero, except for the geometric mean, where those values will be set to the lower limit of quantification.

3.2 Analysis Populations

Analysis populations in this study are defined in the sections that follow.

3.2.1 Safety Population

The Safety Population will include all subjects who receive at least one injection of RA101495.

3.2.2 Efficacy Evaluable Population

The Efficacy Evaluable Population will include all subjects in the Safety Population who complete the 12-week Treatment Period.

3.2.3 Per Protocol Population

The Per Protocol Population will include all subjects in the Safety Population who complete the 12-week Treatment Period and have no major protocol violations.

Protocol violations will be assessed as "minor" or "major" during data review meetings that will take place prior to database lock.

3.2.4 Pharmacokinetic Population

The PK Population will include all subjects in the Safety Population who have at least 1 plasma sample obtained for PK assessment.

3.2.5 Pharmacodynamic Population

The PD Population will include all subjects in the Safety Population who have at least 1 plasma sample obtained for PD assessment.

3.3 Analysis Endpoints

3.3.1 Safety Endpoints

Safety assessments will include evaluation of AEs and SAEs (including major adverse vascular event (MAVE criteria), surgery and other procedures, clinical laboratory tests, ECGs, vital signs, and physical examinations. Safety evaluation will also include a determination of anti-drug antibodies (ADA). Laboratory assessments will include PNH clone size.

3.3.1.1 Injection Site Reactions

The investigator will assess the injection sites at each scheduled visit for:

- Pain, tenderness, erythema, and induration severity (Table 3)
- Erythema and induration: maximum linear diameter
- Blisters, ulceration, necrosis: maximum linear diameter and severity
- Lymphadenopathy (absent, mild, moderate, or severe)

Table 3: Grading the Severity of Local Injection Site Reactions

Local Reaction to Injectable Product	Grade 1 (Mild)	Grade 2 (Moderate)	Grade 3 (Severe)	Grade 4 (Potentially Life Threatening)
Pain	Does not interfere	Repeated use of	Any use of narcotic	Emergency room visit or
	with activity	non-narcotic pain reliever >24 hours or	pain reliever or prevents daily	hospitalization
		interferes with activity	activity	
Tenderness	Mild discomfort to touch	Discomfort with movement	Significant discomfort at rest	Emergency room visit or hospitalization
Erythema/ redness	2.5 to 5.0 cm	5.1 to 10.0 cm	>10.0 cm	Necrosis or exfoliative dermatitis
Induration/ swelling	2.5 to 5.0 cm and does not interfere with activity	5.1 to 10.0 cm or interferes with activity	>10.0 cm or prevents daily activity	Necrosis

The Injection site reactions CRF page has the date of assessment but is not specifically connected to a study visit (even though the assessment is planned to be

done in conjunction with visits). The following algorithm will be used to assign a study visit for each assessment.

```
Assign Baseline if SVD1SDT<=ADT<=SVD1EDT;
else assign 'Week 1' if SVD8SDT<=ADT<=SVD8EDT;
else assign 'Week 2' if SVD15SDT<=ADT<=SVD15EDT;
else assign 'Week 3' if SVD22SDT<=ADT<=SVD22EDT;
else assign 'Week 4' if SVD29SDT<=ADT<=SVD29EDT;
else assign 'Week 6' if SVD43SDT<=ADT<=SVD43EDT;
else assign 'Week 8' if SVD57SDT<=ADT<=SVD57EDT;
else assign 'Week 10' if SVD71SDT<=ADT<=SVD71EDT;
else assign 'Week 12' if SVD84SDT<=ADT<=SVD84EDT. (So if ADT lies within more than one of the visit periods, assign the first one matching)
```

Note: Here SVDxSDT is the SDTM defined "actual start date" of the visit planned for day x, and SVDxEDT the corresponding end date.

3.3.2 Primary Efficacy Endpoint

The primary evaluation period is from Week 6 to Week 12. The primary efficacy endpoint is the change from baseline in serum LDH levels during this period, defined as the mean of the non-missing LDH values of Weeks 6, 8, 10, and 12 minus the baseline LDH value (defined in Section 3.1.3).

Note: This will only include the scheduled assessments, LDH values from unscheduled assessments will only be provided in the listings.

3.3.3 Secondary Efficacy Endpoints

Secondary efficacy variables include the change from baseline values at each of the following scheduled post-baseline assessment time-points:

- total bilirubin
- total hemoglobin,
- free hemoglobin,
- haptoglobin,
- reticulocytes
- hemoglobinuria.

3.3.4 Pharmacodynamic Endpoints

Pharmacodynamic endpoints include:

- Changes from baseline in sRBC lysis for the classical complement pathway
- Changes from baseline in Wieslab ELISA for alternative complement pathway
- Changes from baseline in C5 concentration levels.

3.3.5 Pharmacokinetic Endpoints

Drug exposure in the different cohorts will be evaluated using PK parameters derived from non-compartmental methods. All calculations will be based on actual sampling times. Individual PK parameters will be presented in listings and summarized by cohort using descriptive statistics.

Pharmacokinetic endpoints include:

- Plasma concentrations of RA101495 and its major metabolites (RA103488 and RA102758)
- Maximum plasma concentration (C_{max})
- Time corresponding to C_{max} (t_{max})
- Area under the drug concentration-time curves (AUC_{0-t})
- Plasma concentrations of eculizumab (Cohort B only).

3.3.6 Quality of Life Assessments

Quality of life assessments will be performed according to the Time and Events Table (Table 2). The following QOL questionnaires will be used during this study:

- European Organization for the Research and Treatment of Cancer Quality of Life Questionnaire-C30 (EORTC-QLQ-C30)
- Functional Assessment of Chronic Illness Therapy-Fatigue (FACIT-Fatigue) Scale
- EuroQol-5D (EQ-5D).

3.3.6.1 **EORTC-OLO-C30**

The EORTC QLQ-C30 consists of 30 questions, which are incorporated into 5 functional domains (physical, role, cognitive, emotional, and social domains; see Table 4); a global health status/global QOL scale; 3 symptom scales (fatigue, pain, and nausea and vomiting scales); 6 single items that assess additional symptoms (e.g. dyspnea, appetite loss, sleep disturbance, constipation, and diarrhea); and the

perceived financial burden of illness treatment (Aaronson, 1993; Aaronson, 1996). Subjects answer questions based on symptoms/status over the preceding week.

The QLQ-C30 is composed of both multi-item scales and single-item measures. These include five functional scales, three symptom scales, a global health status / QoL scale, and six single items.

Each of the multi-item scales includes a different set of items - no item occurs in more than one scale.

All of the scales and single-item measures range in score from 0 to 100. A high scale score represents a higher response level.

- a high score for a functional scale represents a high / healthy level of functioning
- a high score for the global health status / QoL represents a high QoL,
- a high score for a symptom scale / item represents a high level of symptomatology / problems.

The principle for scoring these scales is the same in all cases:

- 1) Estimate the average of the items that contribute to the scale; this is the raw score.
- 2) Use a linear transformation to standardize the raw score, so that scores range from 0 to 100; a higher score represents a higher ("better") level of functioning, or a higher ("worse") level of symptoms.

Table 4: Scoring the EORTC QLQ-C30

	Scale	Number of Items	Item Range*	Item Numbers	Functional scales
Global health status / QoL					
Global health status/QoL	QL2	2	6	29, 30	
Functional scales					
Physical functioning	PF2	5	3	1 to 5	F
Role functioning	RF2	2	3	6, 7	F
Emotional functioning	EF	4	3	21 to 24	F
Cognitive functioning	CF	2	3	20, 25	F
Social functioning	SF	2	3	26, 27	F
Symptom scales / items					
Fatigue	FA	3	3	10, 12, 18	
Nausea and vomiting	NV	2	3	14, 15	
Pain	PA	2	3	9, 19	
Dyspnoea	DY	1	3	8	
Insomnia	SL	1	3	11	
Appetite loss	AP	1	3	13	

Constipation	СО	1	3	16	
Diarrhoea	DI	1	3	17	
Financial difficulties	FI	1	3	28	

^{*} Item range is the difference between the possible maximum and the minimum response to individual items; most items take values from 1 to 4, giving *range* = 3. The exceptions are the items contributing to the global health status/QoL, which are 7-point questions with range = 6,

For all scales, the Raw Score is the mean of the component items.

For functional scales the score is:

Score =
$$\{1 - (Raw score - 1)/(range)\} \times 100$$

and for Symptom scales/items and Global health status/QoL:

Score =
$$\{(Raw score - 1)/(range)\} \times 100$$
.

3.3.6.3 EO-5D

The EQ-5D 3 level version [EuroQol, 1990] is a standardized instrument for measuring generic health status. The EQ-5D consists of the EQ-5D descriptive system and the EQ visual analogue scale (VAS). The EQ-5D descriptive system comprises the following five dimensions: mobility, self-care, usual activities, pain/discomfort and anxiety/depression; each dimension has three levels:

Level 1: indicating no problem

Level 2: indicating some problems

Level 3: indicating extreme problems.

For the EQ-5D visual analog scale (VAS) question the patient rates how good or bad their health is today on a 0 - 100 point scale (0 representing worst imaginable health state and 100 representing best imaginable health state).

Note that for the analyses, EQ-5D values coded as "ambiguous" will be mapped to the "missing" category.

3.3.6.4 Treatment Satisfaction Questionnaires

The following treatment satisfaction questionnaire will be administered to Cohort A subjects to assess overall satisfaction with SC administration of the study medication at the end of the 12-week Treatment Period.

"How satisfied are you with the overall method of study medication administration (subcutaneous self-injection)?"

The following more targeted questionnaire will be administered to the Cohort B (Switch) subjects to assess their preference for daily SC self-injection at home compared with biweekly infusions given by a health-care professional in the clinic.

"Overall how satisfied are you with the method of medication administration used in this study (daily subcutaneous self-injection) compared with intravenous eculizumab infusions every 2 weeks?"

Both questions will use the following 5-point Likert response scale:

• Very Dissatisfied=1

- Dissatisfied=2
- Neutral=3
- Satisfied= 4
- Very Satisfied= 5.

3.4 Patients Disposition and Evaluability

3.4.1 Patient Disposition

A disposition of all enrolled subjects will be provided. This will include the number and percentage of patients evaluated for each of the analysis populations (Section 3.2) will be presented by cohort and overall. The number of patients discontinuing from the study and the primary reason for discontinuation will also be summarized.

3.4.2 Protocol Deviations

A listing of protocol deviations will be presented by cohort.

3.5 Demographics and Baseline Characteristics

3.5.1 Demographics

Patient demographics and baseline characteristics will be summarized by cohort and overall for the Safety, Efficacy Evaluable, Per Protocol, and Pharmacodynamic Populations.

Descriptive statistics will be provided for age, height, weight, and body mass index (BMI, calculated as weight in kilograms divided by height in meters squared). Frequencies and percentages will be tabulated for sex, race, and ethnicity.

Age will be calculated as (informed consent date – date of birth + 1)/365.25, truncated and displayed as years. BMI will be calculated as weight (kg)/height² (m²), using the weight and height measurements obtained at screening.

Note: If the date of birth day and month are missing impute January 1st, if only the day is missing impute the 1st.

3.5.2 Medical History

Medical history will be collected and summarized by cohort and overall.

3.5.3 PNH Disease History

The following PNH disease history data will be summarized by cohort and overall.

• Age at initial diagnosis (years)

Age at initial diagnosis will be calculated as (date of initial PNH diagnosis – date of birth + 1)/365.25,

Note: If the day and month are missing for date of initial PNH diagnosis, impute July 2nd, if only the day is missing impute the 15th. If the date of birth day and month are missing impute January 1st, if only the day is missing impute the 1st.

- PNH clone size (% RBC, % WBC)
- Complement C5 gene mutation (Present, Absent, unknown)
- Thrombotic event within 6 months prior to screening (yes, no)
- Blood Transfusion within 6 months prior to screening (yes, no)

3.5.4 PNH Treatment History

The following PNH treatment history data will be summarized by cohort and overall.

- Eculizumab treatment history (note: Cohort B only)
 - o Age at initial eculizumab treatment

Age at initial eculizumab treatment will be calculated as (date of initial eculizumab treatment – date of birth + 1)/365.25,

Note: If the day and month are missing for date of initial eculizumab treatment, impute July 2nd, if only the day is missing impute the 15th. If the date of birth day and month are missing impute January 1st, if only the day is missing impute the 1st.

o Duration of eculizumab treatment (months)

Calculated as:

(stop date of eculizumab treatment – start date of eculizumab treatment+ 1) /(365.25/12)

Note: For stop date and start date, if the day and month are missing impute July 2^{nd} , if only the day is missing impute the 15^{th} . If corresponding duration calculation yields a negative number, impute a value of 1 day = 1/30.4375 months.

o Eculizumab dose, units and frequency will be provided in the listings.

3.6 Prior and Concomitant Medications

Incidence of prior and concomitant medication will be presented by cohort, therapeutic area, and preferred (generic) drug name.

Prior medications are those that started and stopped before exposure to study medication; concomitant medications are all medications taken during the study

period, including those started before but on going at first dose. Where a medication start date is partially or fully missing, and it is unclear as to whether the medication is prior or concomitant, it will be assumed that it is concomitant.

3.7 Exposure to Study Treatment

Prefilled syringes containing RA101495 will be dispensed every 2 weeks. Subjects will also receive a secure container to dispose of used syringes at each visit and should return the used container containing all used syringes. All study drug (syringes) and disposal containers must be returned to the site at the last study visit. Dosing on study visit days will be held until the completion of the PK and PD sample blood collection has been completed.

Treatment duration (number of days patient received study medication) will be described using summary statistics by cohort and overall. Treatment duration will be calculated as the Date of last dose – Date of first dose +1.

The number of patients who had a dose escalation and the number of days from baseline where the dose escalation occurred (Date of dose escalation – date of first dose +1) will summarized by cohort and overall.

These analyses will be performed for the Safety Population.

3.8 Safety Analysis

Safety analysis results will be presented using the Safety Population by cohort and overall.

3.8.1 Adverse Events

All adverse events will be coded using the Medical Dictionary of Regulatory Activities (MedDRA) Version 18.0 or higher and will be classified by MedDRA system organ class (SOC) and preferred term (PT). Analyses of adverse events will be performed using the safety population.

Treatment emergent adverse events (TEAEs) are defined as follows:

- An AE that occurs after treatment start that was not present at the time of treatment start; or
- An AE that increases in severity after treatment start, if the event was present at the time of treatment start.

The following TEAE summaries will be provided:

- Overall summary of Treatment Emergent Adverse Events
- Incidence of Treatment Emergent Adverse Events by System Organ Class and Preferred Term

- Incidence of Treatment Emergent Adverse Events by System Organ Class, Preferred Term, and Maximum Severity
- Incidence of Treatment Emergent Adverse Events by System Organ Class, Preferred Term, and Relationship to Study Drug
- Incidence of Treatment Emergent Adverse Events Leading to Study Discontinuation by System Organ Class and Preferred Term
- Listing of Serious Adverse Events by System Organ Class and Preferred Term.

For these summaries, the number and percentage of patients who experienced at least one of the TEAE as well as the number and percentage of patients who experienced each specific SOC and PT will be presented by cohort. The corresponding number of TEAEs will also be presented.

For the presentation of TEAE incidences, the SOCs will be sorted alphabetically, and within SOC, the preferred term (PT) will be used and presented by decreasing total frequency.

3.8.1.1 Determining Treatment Emergent with Adverse Event Dates

The following rules apply when determining if an AE is treatment-emergent in the scenario where the start date is missing or partially missing. These rules provide an algorithm to "impute" a complete AE start date which will then be used to determine if the AE is treatment emergent.

AE start date missing day and month:

- If the year is the same as the year of the treatment start date, the day and month of the date of treatment start date will be assigned to the missing fields.
- If the year is prior to the year of the treatment start date, December 31 will be assigned to the missing fields.
- If the year is after the year of the date of the treatment start date, January 1 will be assigned to the missing fields.

AE start date missing month only:

• The day will be treated as missing, and both month and day will be replaced according to the above procedure.

AE start date missing day only:

• If the month and year are the same as the month and year of the treatment start date, the day of the treatment start date will be assigned to the missing day.

- If either the year is before the year of the date of the treatment start date or if both years are the same but the month is before the month of the treatment start date, the last day of the month will be assigned to the missing day.
- If either the year is after the year of the treatment start date or if both years are the same but the month is after the month of the treatment start date, the first day of the month will be assigned to the missing day.

AE start date completely missing:

- If the AE end date is complete and after the treatment start date, the treatment start date will be assigned to the missing start date.
- If the end date is complete and before the treatment start date, the end date will be assigned to the missing start date
- Otherwise the AE start date will be assigned the treatment start date.

If the end date is complete and the imputed start date as above is after the end date, the start date will be imputed by the end date.

3.8.2 Adverse Events of Special Interest

3.8.2.1 Thrombotic Adverse Events

A separate table for thrombotic AEs will be presented, summarizing TEAEs by PT for each cohort and overall. The events in Table 6 (MAVE criteria, 2007]) will be evaluated in the assessment of thrombotic AEs.

Table 6: Thrombotic Event Description (MAVE Criteria)

MAVE Criteria	AE Preferred Term Mapping
Thrombophlebitis/Deep vein thrombosis	Preferred Term: 10051055 Deep vein thrombosis Preferred Term: 10043570 Thrombophlebitis
Pulmonary embolus	Preferred Term: 10037377 Pulmonary embolism
Myocardial infarction	Preferred Term: 10028596 Myocardial infarction
Transient ischemic attack	Preferred Term: 10044390 Transient ischaemic attack
Renal vein thrombosis	Preferred Term: 10038548 Renal vein thrombosis
Acute peripheral vascular occlusion	Preferred Term: 10053648 Vascular occlusion
Amputation (non-traumatic, non-diabetic)	Preferred Term: 10061627 Amputation
Mesenteric/Visceral vein thrombosis	Preferred Term: 10027402 Mesenteric vein thrombosis Preferred Term: 10077829 Visceral venous thrombosis
Unstable angina	Preferred Term: 10002388 Angina unstable
Mesenteric/Visceral arterial thrombosis	Preferred Term: 10027397 Mesenteric artery thrombosis Lower level term: 10043611 Thrombosis arterial
Hepatic/Portal vein thrombosis	Preferred Term: 10019713 Hepatic vein thrombosis Preferred Term: 10036206 Portal vein thrombosis
Dermal thrombosis	Lower level term: 10042545 Superficial phlebothrombosis
Gangrene (non-traumatic, non-diabetic)	Preferred Term: 10017711 Gangrene Preferred Term: 10009971 Colon gangrene Preferred Term: 10017954 Gastrointestinal gangrene
Cerebral arterial occlusion/cerebrovascular accident	Preferred Term: 10008190 Cerebrovascular accident Preferred Term: 10008089 Cerebral artery occlusion
Cerebral venous occlusion	Preferred Term: 10076895 Cerebral vascular occlusion
Renal arterial thrombosis	Preferred Term: 10038380 Renal artery thrombosis

Abbreviation: MAVE=major adverse vascular event.

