12.1.3 ADVERSE EVENTS OF SPECIAL INTEREST

12.1.3.1 THROMBOTIC ADVERSE EVENTS

All subjects should be monitored for signs and symptoms of thrombotic events at all study visits (weekly for the first 4 weeks followed by every 2 weeks). The method of diagnosis (e.g. ultrasound, computed tomography [CT], magnetic resonance imaging [MRI], venogram, or other [specify]) for any reported event should be recorded in the eCRF. All AEs should be recorded as AEs per Section 12.1 and Section 12.3.

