13.3.4.2 ADVERSE EVENTS OF SPECIAL INTEREST

13.3.4.2.1 THROMBOTIC ADVERSE EVENTS

Thrombotic AEs will be summarized separately by system organ class, preferred term, and cohort. The events in Table 6 (MAVE criteria [Hillmen 2007]) will be evaluated in the assessment of thrombotic AEs:

Table 6 Thrombotic Event Description (MAVE Criteria)

Thrombophlebitis/Deep vein thrombosis	Mesenteric/Visceral arterial thrombosis
Pulmonary embolus	Hepatic/Portal vein thrombosis
Myocardial infarction	Dermal thrombosis
Transient ischemic attack	Gangrene (non-traumatic, non-diabetic)
Renal vein thrombosis	Cerebral arterial occlusion/cerebrovascular accident
Acute peripheral vascular occlusion	Cerebral venous occlusion
Amputation (non-traumatic, non-diabetic)	Renal arterial thrombosis
Mesenteric/Visceral vein thrombosis	Other
Unstable angina	

Abbreviation: MAVE=major adverse vascular event.

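### SAP Table 6 drops the protocol's *Other* thrombotic category and does not say at which MedDRA level its two lower-level-term entries are selected

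*SAP*

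**What the plan says.** Protocol 13.3.4.2.1 sets the reporting requirement: "Thrombotic AEs will be summarized separately by system organ class, preferred term, and cohort". It then gives Table 6 (MAVE criteria) and says that the events in it "will be evaluated in the assessment of thrombotic AEs". *Other* is one of those categories. The protocol does not define it further.

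SAP 3.8.2.1 implements this: "A separate table for thrombotic AEs will be presented, summarizing TEAEs by PT for each cohort and overall". Its own Table 6 sets each category against one to three MedDRA codes, in a column headed "AE Preferred Term Mapping". It has no *Other* row. Two of the codes are labelled as lower level terms: "Lower level term: 10042545 Superficial phlebothrombosis", which is the whole of the dermal thrombosis row, and "Lower level term: 10043611 Thrombosis arterial", which stands beside one preferred term in the mesenteric/visceral arterial row.

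SAP 3.8.1 classifies adverse events by system organ class and preferred term and names no other analysis level. SAP Section 1 says that its procedures rest on protocol Section 13, where the full Table 6 sits. The thrombotic output is Table 14.3.1.4, by system organ class and preferred term. The accompanying listing is 16.2.10.5.

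**The concern.** Thrombosis is a defining complication of PNH and the first event of special interest in the protocol. Protocol 6.1 stresses that it arises at unusual sites, the dermal veins among them. A fixed code list with no residual category is weakest for such events. The protocol allowed for them with *Other*; the SAP removes it without giving a reason or a review step in its place.

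The second issue is an incomplete selection rule. The summary level and the column heading both point to preferred terms, yet two entries are not preferred terms. Two programmers could build different tables from the same text, and under one reading the dermal row is empty by construction.

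The third is the opposite risk. Some entries are broader than the category they stand for, so the table could also include events that do not meet the criteria.

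**Working it through.** No figure in the plan has to be reproduced here. The check is a row-by-row comparison of the two tables, then a count of entries by MedDRA level.

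**Categories.** Protocol Table 6 has eight rows of two categories plus one single category: 8 × 2 + 1 = 17. SAP Table 6 has 16. The only difference is *Other*; the SAP adds none.

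**Entries in SAP Table 6.**

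| Codes per row | Rows | Entries |
|---|---|---|
| 1 | pulmonary embolus; myocardial infarction; transient ischemic attack; renal vein; acute peripheral occlusion; amputation; unstable angina; dermal; cerebral venous; renal arterial (10 rows) | 10 |
| 2 | thrombophlebitis/deep vein; mesenteric/visceral vein; mesenteric/visceral arterial; hepatic/portal vein; cerebral arterial (5 rows) | 10 |
| 3 | gangrene (1 row) | 3 |
| Total | 16 rows | 23 |

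Of the 23 entries, 2 are lower level terms and 21 are preferred terms.

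**Effect of the selection level on the two rows.**

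| Row | Selected on the labelled level | Selected on preferred-term codes only |
|---|---|---|
| Dermal thrombosis | 1 of 1 entry usable | 0 of 1 |
| Mesenteric/visceral arterial | 2 of 2 | 1 of 2 |

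**Breadth of the entries.** The amputation and gangrene categories carry a non-traumatic, non-diabetic restriction. The codes against them (*Amputation*; *Gangrene*, *Colon gangrene*, *Gastrointestinal gangrene*) do not. *Vascular occlusion* likewise lacks the words acute and peripheral, and *Cerebral vascular occlusion* is not confined to veins.

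**Scale.** One subject wrongly left out of, or put into, the table changes the incidence by 100/n percentage points. The planned sizes are 8–12 in Cohort A, 6–8 in Cohort B and up to 20 overall.

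| n | 100/n |
|---|---|
| 20 | 5.0 |
| 12 | 8.3 |
| 8 | 12.5 |
| 6 | 16.7 |

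**Other events of special interest.** Protocol 13.3.4.2.2, 13.3.4.2.3 and 13.3.4.2.5 each require a separate summary of adverse events: hepatic and biliary, pancreatic, and *Neisseria meningitidis* infection. SAP 3.8.2 covers only thrombotic events and injection site reactions. SAP 3.8.3.1 and 3.8.3.2 grade the liver and pancreatic laboratory values, but the SAP's table list has no adverse event table for any of the three groups.

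**The case against.** The best defence is that summarizing by preferred term describes the display, not the selection. The SAP labels every entry with its level and code, so the two lower level terms can be read as an instruction to select on that level and show the result under the preferred term. MedDRA coding is kept and listed (16.2.10.3), so this is feasible. That stands, and it limits the point: a reader might infer that these entries cannot match anything, but the SAP states no rule that would make this so. What remains is an ambiguity, and only dermal thrombosis depends on it wholly.

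A reader might also infer that the list can only under-count. Dropping *Other* does act in that direction, but the unrestricted amputation and gangrene codes act in the other. No one-way bias is shown.

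Nor would an event outside the list be lost from the report. It stays in the tables of all treatment-emergent events by class, term, severity and relationship, in the adverse event listings and, if serious, in the serious event listing. With up to 20 subjects a careful reader could find it. Whether it would also be missing from listing 16.2.10.5 cannot be said, because only the title of that listing is given.

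Finally, the study is uncontrolled and the thrombotic summary is descriptive; no test depends on it. The 1/n figures hold for any single event and say nothing about how likely a misclassification is. All of this lowers the weight of the point. None of it explains why a category the protocol requires is absent.

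**Conclusion.** The concern holds as a departure from the protocol and an incomplete selection rule, and it should be corrected before lock. One of 17 protocol categories is missing, which leaves 23 codes as the whole definition. One row rests entirely, and another partly, on lower level terms with no stated matching level. At least two categories are mapped without their qualifiers. The consequence is a thrombotic table that may be wrong by 5.0 to 16.7 percentage points for each misclassified subject, depending on the denominator. It is not a loss of events from the report.

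This rests on two assumptions: that SAP Table 6 is what selects events for Table 14.3.1.4 (the table shells are a separate document), and that no review step is specified elsewhere. The empty dermal row is conditional on selection by preferred-term code alone. The validity of the MedDRA codes and their parent terms was not assessed, since that needs the dictionary.

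The omission of the three other event groups is a separate and unconditional gap between SAP 3.8.2 and the protocol.

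**What to change.** In SAP 3.8.2.1:

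1. Restore *Other*. As the protocol leaves it undefined, fill it by a documented medical-monitor review of all treatment-emergent event terms before database lock. The same review confirms that mapped amputation and gangrene events meet the non-traumatic, non-diabetic qualifiers. SAP 3.10 lets the cohorts lock separately, so the review should precede each lock.
2. State that the two lower-level-term entries are selected on the lower-level-term code and displayed under their preferred term.

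In SAP 3.8.2 and the table list, add the hepatic/biliary, pancreatic and *Neisseria meningitidis* adverse event summaries.

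Two alternatives are less sound. Replacing the lower level terms by their parent preferred terms may cast too wide a net, since *Thrombosis arterial* names no mesenteric or visceral site. Using the eCRF diagnosis field as the trigger assumes more than protocol 12.1.3.1 provides: it asks that the method of diagnosis "for any reported event should be recorded in the eCRF", but describes no flag that identifies an event as thrombotic.

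The cost is a few lines of SAP wording, three more tables, and a term review covering up to 20 subjects. No new data are needed.
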